We will perform '3+3' classical dose escalation design to determine DLT. The first 3 patients will receive ENT at dose level 1 (DL1: 8mg on D1, 8 of 21-day cycles). pembrolizumab (MK-3475) will be added starting day 1 cycle 2 at the approved dose (200mg intravenously [IV] over 30 minutes on D1 of 21-day cycles) for 4 cycles. A safety committee that includes the study chair, the principal investigator from any study site that has enrolled a patient on the specific DL, as well as two sub-investigators from Yale will review safety data after enrollment of every 3 patients during the dose escalation phase. The committee will have the discretion to decide to enroll 3 more patients in the specific dose level even if no DLT occurred in the first 3 treated patients in that dose level if there are toxicity/safety concerns that did not qualify as DLT (maximum of 6 evaluable patients to be enrolled at any dose level). The committee can also decide to enroll patients at a lower dose level after the first 3 or after the first 6 patients enrolled in any dose level even if no or one DLT occurred at that dose level if there are toxicity/safety concerns that did not qualify as DLT. The following regarding enrollment in different dose levels will be considered guidance for the safety committee but can be modified in accordance of above: If no patient of the 3 patients treated with combined therapy at DL1 develops DLT, then dose level 2 (DL2) will be tested. DL2 will be with ENT at 8mg on D1, 8 and 15 and pembrolizumab (MK-3475) at 200mg IV on D1 of 21-day cycles. If 1 patient out of the 3 patients has DLT at DL1, we will expand cohort to 3 more patients and if 1 patient of the 6 patients has DLT (i.e. only 0/3 or 1/6), we will test next dose (DL2). If no patient of the 3 patients treated with combined therapy at DL2 develop DLT, then DL2 will be used for part 2 (expansion cohort). If 1 patient out of the 3 patients has DLT at DL2, we will expand cohort to 3 more patients and if 1 patient of the 6 patients has DLT (i.e. only 0/3 or 1/6), dose level 2 (DL2) will be used for part 2 (expansion cohort). If 2 patients or more of the 6 patients at DL2 experience DLT, DL1 will be used for expansion cohort. The cycle duration will be 21 days, the maximum number of treatment cycles of entinostat will be 18 cycles and for pembrolizumab (MK-3475) the maximum number of cycles will be 17. Cycle 2 to cycle 18, will have concurrent administration. In all the phases of the study, entinostat will be administered in clinic within 2 hours before administration of pembrolizumab (MK-3475). Entinostat will be stored at the pharmacy and it will not be given for the patient to take home.

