- Pregnant or breast-feeding females (lactating females must agree not to breast feed while taking the study drugs)
- Use of any other experimental drug or therapy within 21 days of baseline - patients who have had chemotherapy or radiotherapy within 4 weeks of entering the study or those who have not recovered from adverse events due to agents administered more than 4 weeks earlier
- Known hypersensitivity to pembrolizumab (MK-3475) or entinostat or history of allergic reactions to compounds of similar chemical or biologic composition to anti-PD1 antibodies or entinostat.
- Prior treatment with any anti-PD-1 blocking therapies or HDACi, or anti-CTLA-4 antibody, CD137 agonist or other immune activating therapy such as anti-CD 40 antibody within the last 3 months of enrollment in the study.
- Any history of active or severe autoimmune disease including:
 - Inflammatory bowel disease, including ulcerative colitis and Crohn's Disease
 - Rheumatoid arthritis, systemic progressive scleroderma, systemic lupus erythematosus, autoimmune vasculitis (e.g., Wegener's Granulomatosis).
 - Note: patients with hypothyroidism who are on stable doses of hormone replacement therapy are allowed
- CNS or motor neuropathy considered of autoimmune origin (e.g. Guillain-Barre Syndrome, myasthenia gravis, multiple sclerosis)

Has a history of (non-infectious) pneumonitis that required steroids or has current pneumonitisPatients who are Human Immunodeficiency Virus (HIV) positive may participate IF they meet the following eligibility requirements: They must be stable on their anti-retroviral regimen, and they must be healthy from an HIV perspective.

They must have a CD4 count of greater than 250 cells/mcL.

They must not be receiving prophylactic therapy for an opportunistic infection.

Intervention and Mode of Delivery: Entinostat, PO administration, pembrolizumab (MK-3475), IV infusion

Duration of Intervention and Evaluation: 1 year or until disease is progressed

Statistical Methods:

(a) Definition of primary outcome/endpoint: The primary endpoint is the maximum tolerated dose (MTD), which is the highest dose level where 1 or fewer of 6 participants experience a dose limiting toxicity (DLT) during the first two cycles of treatment. The RP2D is the same as the MTD. The maximally administered dose is the dose at which two or more of 6 participants experience a DLT.

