5.1.3 Other Modality(ies) or Procedures: N/A

5.2 **Definition of Dose-Limiting Toxicity**

The primary endpoint is the maximum tolerated dose (MTD), which is the highest dose level where 1 or fewer of 6 participants experience a dose limiting toxicity (DLT) during the first two combined cycles of treatment. The recommend phase 2 dose (RP2D) is the same as the MTD.

NCI Protocol #:10009

Version Date: 09/04/2020

The maximally administered dose is the dose at which two or more of 6 participants experience a

DLT.

DLT will be defined as the occurrence of any of the following during the first 2 cycles of combined therapy unless the event can clearly be determined to be unrelated to the study drugs.

- Any grade 3 or 4 non-hematologic toxicity with the following exceptions: A) Transient laboratory abnormalities that can be treated or resolve to grade 2 or less within 72 hours.
- Grade 4 hematologic toxicity, including treatment-associated aplasia lasting >42 days from the last dose of study drug. Given that severe anemia, neutropenia and thrombocytopenia are features of advanced MDS and commonly encountered in this patient population, they will not be used to define DLT except if associated with prolonged treatment-associated aplasia as described above.
- Patients with grade 3 immune related adverse events will be removed from the treatment and this will be considered to be a DLT as well as any other immune-related adverse event that results in pembrolizumab interruption, dose modification, or discontinuation of therapy.

Participants who do not complete the first 2 cycles of combined therapy without experiencing a DLT (as DLT period is defined in the first 2 combined therapy cycles) during dose escalation will also be replaced. To be DLT-evaluable, the patient must complete the first two cycles of combined therapy without experiencing a DLT. Any patient who is dose reduced during the entinostat run-in first cycle due to entinostat-related toxicity will be analyzed on the dose level that corresponds to the reduced dose level delivered during the first cycle of combined therapy.

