A safety committee that includes the study chair, the principal investigator from any study site that has enrolled a patient on the specific DL, as well as two sub-investigators from Yale will review safety data after enrollment of every 3 patients during the dose escalation phase. The committee will have the discretion to decide to enroll 3 more patients in the specific dose level even if no DLT occurred in the first 3 treated patients in that dose level if there are toxicity/safety concerns that did not qualify as DLT (maximum of 6 evaluable patients to be enrolled at any dose level). The committee can also decide to enroll patients at a lower dose level after the first 3 or after the first 6 patients enrolled in any dose level even if no or one DLT occurred at that dose level if there are toxicity/safety concerns that did not qualify as DLT. The following regarding enrollment in different dose levels will be considered guidance for the safety committee but can be modified in accordance of above. Dose escalation will proceed within each cohort according to the following scheme.

Number of Patients with DLT at a Given Dose Level	Escalation Decision Rule
0 out of 3	Enter 3 patients at the next dose level.
≥ 2	Dose escalation will be stopped. This dose level will be declared the maximally administered dose (highest dose administered). Three (3) additional patients will be entered at the next lowest dose level if only 3 patients

	were treated previously at that dose.
1 out of 3	
Enter at least 3 more patients at this dose level.
 
• If 0 of these 3 patients experience DLT, proceed to the next dose level.• If 1 or more of this group suffer DLT, then dose escalation is stopped, and this dose is declared the maximally administered dose. Three (3) additional patients will be entered at the next lowest dose level if only 3 patients were treated previously at that dose.
≤ 1 out of 6 at highest dose level below the maximally administered dose	This is generally the recommended phase 2 dose (RP2D)= MTD. At least 6 patients must be entered at the recommended phase 2 dose (RP2D).

Management and dose modifications associated with the above adverse events are outlined in [Section 6](#).

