5.3 Dose Expansion Cohorts

Once the RP2D is reached, an additional 15 patients will be treated at this dose. For the expansion cohort, patients will continue to be monitored for occurrence of DLT. Participants who go off-study during the 1st cycle of entinostat will be replaced in the escalation phase. Participants who do not complete the first 2 cycles of combined therapy without experiencing a DLT (as DLT period is defined in the first 2 combined therapy cycles) will also be replaced. To be DLT-evaluable, the patient must complete the first two cycles of combined therapy without experiencing a DLT. Any patient who is dose reduced during the entinostat run-in first cycle due to entinostat-related toxicity will be analyzed on the dose level that corresponds to the reduced dose level delivered during the first cycle of combined therapy.

The following early stopping rule for excess toxicity in the expansion cohort will be used: We will cease enrollment in the expansion phase at the dose determined from dose escalation part of the study if we observe two or more DLTs among the first six evaluable patients enrolled in the expansion cohort. An evaluable patient is any patient who received a study drug. If the true toxicity rate is 50% or greater at the MTD then this rule will stop the trial with probability at least .89. Similarly, if the true toxicity rate is 33% at the MTD then this stopping rule will end the trial with probability .65. In that event, a new expansion cohort will start at the dose level immediately below the dose level that was expanded. If the dose level being expanded is dose level -1, then the study will be terminated.

Monitoring of all safety and toxicity data is done by the Principal Investigator and the Corresponding Organization on a real-time basis as data are entered into Medidata Rave using the Web Reporting Module. All participating sites are expected to notify the Principal Investigator when a DLT has occurred.

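### The DLT-evaluable definition leaves out the patients who have a DLT, and the expansion stopping rule uses a different set for which .89 and .65 need an unstated condition

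*Combined protocol and SAP*

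**What the plan says.** **Evaluability.** Section 5.2 says: "To be DLT-evaluable, the patient must complete the first two cycles of combined therapy without experiencing a DLT". The same sentence is in the Synopsis (Study Design, Part 2), Section 5.3 and Section 13.1.

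**Replacement.** The sentence before it in Section 5.2 begins "Participants who do not complete the first 2 cycles of combined therapy without experiencing a DLT" and says that such patients are replaced. The Synopsis and Sections 5.2 and 13.1 limit this to dose escalation. Section 5.3, on expansion, omits that limit: "without experiencing a DLT (as DLT period is defined in the first 2 combined therapy cycles) will also be replaced".

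**Primary endpoint.** Section 5.2 and the Synopsis (Statistical Methods) define the MTD as the "highest dose level where 1 or fewer of 6 participants experience a dose limiting toxicity (DLT") and add: "The maximally administered dose is the dose at which two or more of 6 participants experience a DLT".

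**Escalation.** The Synopsis and Sections 5.1 and 13.1 say: "If 1 patient out of the 3 patients has DLT at DL1, we will expand cohort to 3 more patients". The table in Section 5.2 says of those three further patients: "If 1 or more of this group suffer DLT, then dose escalation is stopped". The same sections set a "maximum of 6 evaluable patients to be enrolled at any dose level".

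**Expansion.** The Synopsis and Sections 5.3, 12.1 and 13.1 stop enrollment at the expanded dose if two or more of the first six evaluable patients have a DLT. Each place then says that, for this rule, a patient is evaluable once given a study drug. The stated stopping probabilities are at least .89 at a true toxicity rate of 50% or more, and .65 at 33%.

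**The concern.** An evaluable set that requires freedom from DLT cannot supply a count of DLTs. The MTD is the primary endpoint and fixes the expansion dose, and no section states the rule that must be intended: a patient is evaluable if a DLT occurs or if the window is completed without one.

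The replacement sentence adds to the difficulty. It can mean that non-completers who had no DLT are replaced, or that anyone who did not finish free of DLT is replaced. On the second reading a patient with a DLT is replaced and does not count towards the cap of six evaluable patients.

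In expansion the question is different. Section 5.1.1 starts pembrolizumab in Cycle 2, and Section 5.2 places the DLT window in the first two combined cycles. A patient who leaves in Cycle 1 has been given a study drug and takes one of the six places, but was never at risk of a DLT as defined. At stake is whether the quoted stopping probabilities describe the rule as it will run.

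**Working it through.** **1. Who is in which set**

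| Patient | DLT-evaluable sentence | MTD and escalation counts | Expansion stopping set |
|---|---|---|---|
| DLT in the first two combined cycles | Out | Counted as a DLT | In |
| Completes both cycles, no DLT | In | Counted as no DLT | In |
| Starts the combination, leaves before the window ends, no DLT | Out | Replaced in escalation | In |
| Leaves in the entinostat-only Cycle 1 | Out | Replaced in escalation | In |

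The first row is the contradiction: the first and second columns cannot both hold. The last two rows are the expansion issue. The stopping rule's own definition keeps these patients in the six, including any who are replaced.

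**2. Effect on the cap**

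Suppose six patients are treated at a level and one has a DLT. Under the evaluability sentence 6 − 1 = 5 are evaluable, one short of the cap. If the patient with the DLT is also replaced, a seventh patient could be treated, and the text would not say whether the result is one in six or one in seven.

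**3. The plan's stopping probabilities**

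Inputs from Section 5.3: six patients, stop at two or more DLTs, true rates p of 50% and 33%. With n patients observed, P(stop) = 1 − (1−p)^n − n·p·(1−p)^(n−1).

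- n = 6, p = 1/2: 1 − 1/64 − 6/64 = 57/64 = .8906 (stated .89).
- n = 6, p = 1/3: 1 − 64/729 − 192/729 = 473/729 = .6488 (stated .65). At p = .33 exactly it is .6422.

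Both figures reproduce. They treat all six patients as able to contribute a DLT at rate p.

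**4. If some of the six are unobserved**

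The documents give no drop-out rate, so the number unobserved is an assumption. Two further assumptions are that p is the rate per at-risk patient and that an unobserved patient is scored as no DLT.

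- One unobserved (n = 5): at 1/2, 1 − 6/32 = 13/16 = .8125; at 1/3, 1 − 112/243 = 131/243 = .5391.
- Two unobserved (n = 4): at 1/2, 1 − 5/16 = 11/16 = .6875; at 1/3, 1 − 48/81 = 11/27 = .4074.

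The same point can be put as a share d of treated patients who are lost before being at risk, replacing p by p(1−d) with n = 6. For d = 10% this gives .836 and .580; for d = 20%, .767 and .505. If the 50% and 33% already are rates per treated patient, they play the part of p(1−d), and .89 and .65 stand unchanged.

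**The case against.** The strongest reply is that the operative rules can be followed without the faulty sentence. The MTD definitions count participants, the escalation text counts patients, and the table in Section 5.2 is keyed to the number of patients with a DLT. In escalation the word evaluable enters only through the cap of six. This stands. A reader might infer from the evaluability sentence that every dose level would pass with certainty. That requires putting DLT-evaluable into rules that do not use it, against explicit instructions for one DLT in three.

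The same holds for expansion. A reader might infer that the stopping rule could never trigger because DLT-evaluable patients have no DLTs, or that Section 5.3 leaves open whether a replaced patient keeps a place among the six. Neither is supported. The rule has its own definition, and a replaced patient who was given a study drug counts.

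An all-treated denominator is also a legitimate choice for a safety rule, and the plan does not say that its toxicity rate is conditional on completing the window. On a per-treated reading the figures are exact. That stands too, but the plan does not say that this reading is meant.

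Finally, replacement in expansion rests on Section 5.3 omitting a limit found in the other three copies, which is weak evidence of intent. The expansion point does not depend on it: a patient lost early occupies a place whether or not a replacement is enrolled.

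What the reply does not answer is that the evaluability sentence is wrong as written in four places, and that no section states the intended rule.

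**Conclusion.** The point holds in two parts of different weight.

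First, the DLT-evaluable sentence contradicts the primary-endpoint definitions and the escalation rules, and it leaves replacement and the cap of six open to a reading that sets aside patients with a DLT. The intended count is plain, so this is a drafting error that needs correction; it does not show that the escalation cannot work.

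Second, .89 and .65 are arithmetically correct but rest on a condition that is not stated: all six patients are observed through the window or have a DLT, or the rate is per treated patient. If neither applies, the rule stops less often than stated: .81 and .54 with one of six unobserved, .69 and .41 with two. These figures are illustrations under the assumptions above, not forecasts. Some early loss is plausible, since Section 5.6 cites a median survival of 5 months after azacitidine or decitabine failure, but the documents give no rate. Real-time DLT monitoring (Section 5.3) and the regular calls and the delayed-toxicity rule (Section 12.1) are safeguards, but they do not resolve either wording problem.

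**What to change.** In the Synopsis and Sections 5.2, 5.3 and 13.1, define a DLT-evaluable patient as one who has a DLT in the first two combined cycles or completes both without one. Replace only non-completers who had no DLT. Use this set for the MTD and for the cap of six, and say in Section 5.3 whether replacement applies in expansion.

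For the stopping rule (Synopsis and Sections 5.3, 12.1 and 13.1), choose one of two options:

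- use the same DLT-evaluable set for the first six places, with two DLTs still triggering the stop as soon as they are observed; or
- keep the treated set and state that .89 and .65 assume all six are observed through the DLT window or have a DLT, or that the rate is per treated patient.

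The evaluability correction and the second option change wording only. The first option changes who fills the six places, so the six-patient assessment may finish slightly later while a replacement is observed. The plan should then also say how replacements count against the enrollment ceiling of 27.

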
An additional dose level (DL -1) in which day 8 of ENT will be omitted (i.e. ENT at 8mg on D1, and pembrolizumab (MK-3475) at 200mg IV on D1 of 21-day cycles) will be used if 2 or more patients develop DLT during the first 2 cycles of combined therapy at DL1. If 0 or 1 patients of the 6 patients treated with combined therapy at DL-1 develop DLT then DL-1 will be used in the second part of the study. If 2 or more 6 patients enrolled in DL -1 develop DLT, then the study will be terminated. If the AE drug causality is clear (e.g. immune related event) and one of the drugs is discontinued, the patient can remain on the study and receive the non-causative agent.

Toxicities will be tabulated and graded according to the Common Terminology Criteria for Adverse Events Version 5 (CTCAE-5). DLT will be assessed after the first 2 cycles of combined therapy. Responses will be as defined by International Working Group (IWG)-2006 criteria (CR, PR, or HI) and

[figure not shown]
assessed at the end of combined first 2 cycles, and every 2 cycles afterwards. Patients who achieve an objective response or maintain a stable disease (SD) status after the first 4 combination cycles will continue receiving both drugs at the same schedule till progression or up to 1 year of combined therapy.

PART 2: After the safe dose of the combination is established, 15 patients will be treated with ENT+ pembrolizumab (MK-3475) combination at that same dose and schedule. Participants who go off-study during the 1st cycle of entinostat will be replaced in the escalation phase. Participants who do not complete the first 2 cycles of combined therapy without experiencing a DLT (as DLT period is defined in the first 2 combined therapy cycles) during dose escalation will also be replaced. To be DLT-evaluable, the patient must complete the first two cycles of combined therapy without experiencing a DLT. Any patient who is dose reduced during the entinostat run-in first cycle due to entinostat-related toxicity will be analyzed on the dose level that corresponds to the reduced dose level delivered during the first cycle of combined therapy.

[figure not shown]

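### The formal DLT tally leaves out run-in intolerance at the assigned entinostat level, which can favour a higher MTD; results should also be shown by assigned level

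*Combined protocol and SAP*

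**What the plan says.** Three rules act together.

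- **Window.** Section 5.2: "DLT will be defined as the occurrence of any of the following during the first 2 cycles of combined therapy". The same section defines the MTD as follows: "highest dose level where 1 or fewer of 6 participants experience a dose limiting toxicity (DLT) during the first two combined cycles of treatment". Cycle 1, entinostat alone, lies outside this window.
- **Replacement.** Synopsis Part 2 and Section 5.3: "Participants who go off-study during the 1st cycle of entinostat will be replaced in the escalation phase".
- **Re-attribution.** A patient whose entinostat was lowered in cycle 1 because of its toxicity "will be analyzed on the dose level that corresponds to the reduced dose level delivered during the first cycle of combined therapy". The rule appears in Synopsis Part 2 and in Sections 5.2, 5.3 and 13.1.

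There is a counterweight. The Synopsis and Sections 5.1, 5.2 and 13.1 make the 3+3 rules guidance that the safety committee can modify. In Section 5.2: "The committee can also decide to enroll patients at a lower dose level after the first 3 or after the first 6 patients enrolled" at any level, even with no DLT or one, "if there are toxicity/safety concerns that did not qualify as DLT". The committee may also add three patients for such concerns.

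Two places do not fit these rules. Synopsis Part 2 describes the DLT-observing period as the monotherapy cycle plus two combined cycles. The dosing legend in Section 10 gives cycle 1 entinostat on days 1, 8 and 15 with no reference to dose level, whereas the Synopsis and Section 5.1 give DL1 as days 1 and 8.

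**The concern.** The three dose levels differ only in the entinostat schedule, so intolerance of entinostat is what should separate them. Yet a patient who cannot tolerate the assigned schedule in cycle 1 either is replaced or is counted elsewhere. The formal denominator at a level then consists of patients who got through the run-in on that schedule.

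The exclusion is not confined to minor toxicity. Under Section 6.1.3, grade 3 nausea, vomiting or diarrhea leads to a hold and, if indicated, resumption one level lower; grade 4 takes the patient off protocol therapy. Section 5.2 would count the same drug-related event as a DLT in the first combined cycle. In the run-in it adds nothing to the assigned level.

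Section 1.1 asks for safety, tolerability and the MTD of entinostat given with pembrolizumab. If a later trial starts new patients at the chosen level, those who fail in the first three weeks matter to it, and the formal MTD count does not show them.

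**Working it through.** **Plan's own figures.** The only stated probabilities that depend on DLT counting are those of the expansion stopping rule (two or more DLTs in six, Section 5.3).

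- At 50%: 1 − .5^6 − 6(.5)^6 = .891 (stated: at least .89).
- At 33%: 1 − (1−p)^6 − 6p(1−p)^5 = .642 with p = .33 and .649 with p = 1/3 (stated: .65).

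Both reproduce. The plan gives no operating characteristics for the 3+3 part and no expected rate of run-in reduction.

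**Inputs.** The escalation rule comes from Section 5.2: pass on 0/3, or on 1/3 followed by 0/3. The combined-cycle DLT rate p and the run-in intolerance rate q (reduction or withdrawal for toxicity) are assumptions.

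**Formulas.** Pass probability: f(p) = (1−p)^3 + 3p(1−p)^5. If every run-in reduction or withdrawal counted at the assigned level, and run-in intolerance and later DLT were independent, p would become q + (1−q)p.

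With p = .20:

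| q | event rate | pass probability |
|---|---|---|
| as written | .20 | .512 + .197 = .709 |
| 10% | .10 + .90×.20 = .28 | .373 + .163 = .536 |
| 20% | .20 + .80×.20 = .36 | .262 + .116 = .378 |
| 30% | .30 + .70×.20 = .44 | .176 + .073 = .248 |

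For p between 10% and 33%, the drop is about 6 to 9 points at q = 5% and 12 to 18 points at q = 10%.

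**What this comparison is.** It sets two endpoints side by side: DLT in the combined cycles, and intolerance at any point from the start of cycle 1. It does not measure bias in the plan's own endpoint. For that endpoint, removing run-in failures leaves the DLT rate among those kept unchanged if the two are independent. It lowers that rate only if they are positively related.

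**Illustration of a positive relation (all values assumed).** Suppose 30% of patients are frail, with DLT rates of 60% in the frail and 10% in the rest, and half of the frail are reduced in the run-in.

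- Overall DLT rate: .3×.6 + .7×.1 = .25.
- Frail share among those kept: .15/.85 = .176.
- DLT rate among those kept: .176×.6 + .824×.1 = .188.
- Pass probability: f(.188) = .734, against f(.25) = .600.

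**Attribution.** If the Section 10 legend is followed, a DL1 patient's cycle 1 is on days 1, 8 and 15. Run-in toxicity in that patient did not arise on the DL1 schedule, and the level to which it belongs is unclear until the passages are reconciled.

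**The case against.** A reader might infer that run-in intolerance never counts against a level and that the MTD is therefore biased upward. The documents do not support either statement.

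- **Never counts.** The committee may hold, expand or step down for toxicity that is not a DLT, and the Synopsis describes a formal safety assessment for each level that spans the monotherapy cycle. This stands. The discretion, however, has no threshold for run-in reductions, and nothing requires the committee to see them by assigned level.
- **Biased upward.** The MTD is defined on combined-cycle DLTs. A patient who took the lower schedule in those cycles does inform that lower level. This stands too: an upward shift needs either a whole-regimen question or a positive relation between run-in intolerance and later DLT.
- **Size.** The rates are assumed, and not every reduction is equivalent to a DLT. Section 6.1.3 allows one for grade 2 non-hematologic toxicity unresolved after a week, and its guidance for cytopenias also includes reductions, although Section 5.2 mostly keeps cytopenias out of the DLT definition.
- **Counts such as 2/7.** A patient moved into a level already at six could produce this, and a reader might infer that no rule covers it. The escalation table in Section 5.2 has a row for two or more DLTs with no denominator, and the cap is worded as a "maximum of 6 evaluable patients to be enrolled at any dose level", which limits enrolment. What the plan leaves open is the effect of a moved patient on a level already decided, whether the vacated slot is refilled, and how a DL1 patient reduced to an unopened DL-1 is used.
- **Expansion.** A reader might infer that reduced patients drop out of the efficacy analysis. Section 13.5.2 keeps all eligible patients in the main response analysis. The expansion stopping rule still counts only DLTs, so run-in intolerance does not trigger it.
- **Counting run-in reductions as events.** This would redefine the primary endpoint. It is a debatable trade-off, and the point does not depend on it.

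**Conclusion.** The concern holds in a limited form. Through the window, replacement and re-attribution rules together, the formal DLT tally contains no trace of run-in intolerance at the assigned level, even for events of a grade that would be a DLT one cycle later. This can favour a higher MTD under the two conditions named above, and only unstructured committee discretion works against it.

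The actual size cannot be derived from the documents. The .71 against .54 to .25 comparison rests on assumed run-in rates of 10% to 30%, an assumed 20% combined-cycle DLT rate and independence. It bounds the effect from above at those rates, because it treats every reduction or withdrawal as an event and ignores the committee. The point merits a change because a stated rule creates the selection and one table would expose it.

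**What to change.** 1. Keep the as-treated DLT analysis as it is.
2. Add a table by assigned level, with everyone who started cycle 1 at that level in the denominator: run-in toxicity by grade, reductions, withdrawals and later DLTs. Give it to the safety committee before each escalation decision and report it with the MTD.
3. Add a sensitivity DLT count by assigned level.
4. State how a moved patient affects a level already decided, and whether the vacated slot is refilled.
5. Reconcile the Synopsis description of the DLT-observing period with Section 5.2, and the cycle 1 schedule in Section 10 with the Synopsis and Section 5.1, so that run-in toxicity can be attributed to a level.

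The cost is protocol and SAP wording and one more table. The MTD may look less favourable when shown this way. No dose and no change to the DLT definition is proposed.
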